2.2 Pain Acceptance and Clinical Success Evaluation Criteria

2.2.1 Wong Baker Pain Rating Scale

The Wong-Baker Pain Rating Scale pain scale was developed by Donna Wong and Connie Baker. It can be used from the age of 3. It consists of 6 face shapes that express the pain condition. In a study, it was concluded that the Wong-Baker pain scale was more understandable than the VAS scale in children aged 3-14.¹²

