2.2.3 Complications of Anesthesia

Complications related to the tissue may be observed after anesthesia. These complications are listed below:

- 1- Hematoma
- 2- Pain
- 3- Needle breakage
- 4- Infection
- 5- Emphysema
- 6- Inadequate anesthesia
- 7- Palatal mucosa necrosis

Complications that may be observed after two different anesthesia systems are applied will be recorded.

3. PURPOSE OF THE PROJECT:

3.1. Main Purpose of the Project:

Palatal injection, which is routinely used in the extraction of primary molars, causes pain and fear due to the tight connection between the palatal mucosa and bone, and causes difficulty in tolerating by pediatric patients. The purpose of our study is to evaluate Comfort-In™ Needle-Free Injection in terms of pain perception in children in palatal infiltration anesthesia applied to the upper jaw, which is difficult to tolerate by patients.

4. MATERIALS AND METHODS OF THE RESEARCH:

The required number of participants was obtained after power analysis based on the data of a previously conducted study on the subject [alpha(α)=0.05 beta(β)=0.05 and power=0.95]. Considering that 60 people

should be included in the study and the possibility of loss, the sample size was determined as 90.¹⁴

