The groups will be formed according to the split mouth method in the same patient with symmetrical primary molar teeth. In all groups, "Ultrave D-S Forte 80 mg + 0.03638 mg/ 2 mL (Articaine hydrochloride Epinephrine bitartrate)" will be used as a local anesthetic. In the study group, teeth will be extracted using Comfort-In™ Needle-Free Injection with a single point palatal injection. In the control group, teeth will be extracted using a single point standard injection. Parents of patients who are considered to participate in the study will have their consent forms filled out and a previously prepared informed consent form will be obtained. Children who have planned extraction treatment for maxillary primary molars, have symmetrical teeth, do not have any systemic disease, and whose parents can give consent will be included in the study. Necessary anesthesia will be applied before the extraction procedure and the tooth will be extracted. In patients who are anesthetized with Comfort-In™ Needle-Free Injection during the procedure, if they feel serious pain, the procedure will not be continued and the patient will be excluded from the study. After the anesthesia procedure, the patient will be able to mark the pain level using the Wong Baker Pain Rating Scale. The FLACC test will be evaluated with the video taken during the anesthesia procedure. The obtained data will be evaluated with descriptive and explanatory statistics using the SPSS package program. Anova test and Post Hoc Tukey test will be used for comparison between groups, and an independent two-group t test will be used to evaluate the pain level between male and female patients within groups.

In the volunteer group to which the drug is applied with the "Comfort-in Needle Injection", if the anesthesia procedure is insufficient and/or does not occur, the patient will be given the traditional injection method as a rescue treatment and the patient will be excluded from the study, but the treatment will continue.

A guarantee will be given that the personal data collected will be collected and processed in accordance with the Personal Data Protection Law No. 6698, will not be used or shared for any purpose other than the purpose of collection/processing, that the data will be destroyed when the volunteer withdraws his/her consent, the research ends or the processing of personal data ends, and that the collected personal data will not be shared.

4.1. Location of the Research:

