Children aged 4-11 years who do not have any systemic disease and who apply to the Department of Pedodontics of Necmettin Erbakan University Faculty of Dentistry are planned to be included in our study.

4.2. Time of the Research:

It is planned to be held between 01.02.2024 - 01.08.2024.

4.3. Research Universe, Sample, Research Group:

Children between the ages of 4 and 11 who apply to the Department of Pedodontics, Faculty of Dentistry, Necmettin Erbakan University, and who do not have any systemic diseases will be included in our study. The groups will be formed according to the split mouth method, with symmetrical primary molar teeth in the same patient. Teeth in the study group will be extracted with Comfort-In™ Needle-Free Injection. Standard injection will be applied for teeth extraction in the control group.

Inclusion criteria for the study;

Patients;

- Between the ages of 4-11
- Bilateral maxillary primary molars with an indication for extraction
- Have not taken any analgesics up to 12 hours before treatment
- Have not used antibiotics in the last month
- Teeth with no more than 1/2 of the root physiologically resorbed
- Systematically healthy children
- Those who agree to participate in the study
- Must show a score of 3-4 or 1-2 according to the Frankle Behavior Scale
- Frankle 1: Patients who refuse treatment, cry, are excessively anxious or show signs of severe negative behavior
- Frankle 2: Patients who are non-compliant, unwilling to treat, show vague signs of negative behavior, are sullen but do not express anxiety
- Frankle 3: Patients who accept treatment, are compliant, shy, establish a relationship with the physician but approach it in a measured manner
- Frankle 4: Patients who cooperate with the physician, are curious about treatment, smile and are happy with the environment Frankle(1962)

Teeth;

- Bilateral maxillary primary molars with extraction indication

4.4. Type of Research:

Prospective, experimental, randomized clinical trial

4.5. Manpower Required for Research:

Assistant [name] [name] (Project manager, creation of research design, clinical evaluation, data analysis and study writing)

Dt. [name] (Assistant researcher, routine patient follow-up, application of extraction treatment, data analysis and study writing)

4.6. Data Collection Tools of the Research:

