4.6.1. General Method

This study will be conducted by including children between the ages of 4-11 who apply to the Department of Pedodontics, Faculty of Dentistry, Necmettin Erbakan University, and who do not have any systemic diseases. The required number of participants was obtained after power analysis based on the data of a previously conducted study on the subject [$\alpha=0.05$, $\beta=0.05$ and $\text{power}=0.95$]. Considering that 60 people should be included in the study and the possibility of loss, the sample size was determined as 90.¹⁴

Patients who apply to the Department of Pedodontics, Faculty of Dentistry, Necmettin Erbakan University, meet the inclusion criteria and will be offered to participate in the study if they give their consent to the informed consent form.

The study and control groups will be determined randomly in order to eliminate variables that may cause differences in patients over time. Randomization will be done through the website "randomizer.org". Before starting the study, patients and their parents will be informed about the treatment procedure to be applied.

Systemic and dental history will be taken from the patients before starting the extraction procedure. After clinical examination with inspection, palpation and percussion, periodontal and radiographic examination will be performed. Patients who meet the inclusion criteria will be informed about the study and their written informed consent will be obtained. Since gender is one of the factors that can affect postoperative pain, female and male patients will be distributed equally. Postoperative pain will be assessed using the Wong Baker Pain Rating Scale, where the patient can mark the pain level after the anesthesia procedure. The FLACC test will be evaluated with the video taken during the anesthesia procedure. Later, statistical evaluations and comparisons between groups will be made.

4.6.1. Components of a Study-Specific Clinical Assessment:

Sociodemographic form: This is a sociodemographic information form prepared by the researchers that includes information such as age, gender, contact information, and medical condition of the patients.

Tooth-material information form: This is a form prepared by the researchers that records which teeth were included in the study and the file system used on the teeth.

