FLACC Scale: This is the form where the pain status is recorded using the FLACC scale at the end of the procedure for the teeth included in the study prepared by the researchers. This scale will be evaluated by looking at the video recording taken during palatal anesthesia of the upper primary molar teeth that need to be extracted. The tooth will be extracted after anesthesia.

Wong Baker Pain Rating Scale: This is a form that records the pain status of the teeth included in the study, prepared by the researchers, using the Wong Baker Pain Scale at the end of the procedure. This scale will be used immediately after the palatal anesthesia of the upper primary molars that need to be extracted. The tooth will be extracted after anesthesia.

Dental Anxiety and Fear Index (IDAF-4C): The four components covered by the measure include

emotional, behavioral, physiological, and cognitive modules, and a basic fear module.15 This index will be administered to the patient before anesthesia. After anesthesia, the tooth will be extracted.

4.7. 4.7. Evaluation of Data:

The data obtained as a result of our study will be evaluated with the help of SPSS package program. Postoperative pain will be evaluated using Wong Baker Pain Rating Scale, where the patient can mark the pain status after the anesthesia procedure. FLACC test will be evaluated with the video taken during the anesthesia procedure. The obtained data will be evaluated with descriptive and explanatory statistics with the help of SPSS package program. Anova test and Post Hoc Tukey test will be used for comparison between groups, and independent two-group t test will be used to evaluate the pain status between male and female patients within the groups.

RESOURCES:

- 1-Önçağ Ö., & Çoğulu D. Ailenin Sosyoekonomik Durumu ve Eğitim Düzeyinin Çocuklarda Dental Kaygı Üzerine Etkisi.
- 2-Kleinknecht R. A., Klepac R. K., & Alexander L. D. (1973). Origins and characteristics of fear of dentistry. The Journal of the American Dental Association, 86(4), 842- 848.
- 3-Yardımcı S. (2018). Çocuklarda İnfiltratif Anestezi Yöntemi ile Tek Diş Anestezi (STA) Tekniğinin Karşılaştırılması. (Doktora tezi), İstanbul Üniversitesi.
- 4-<http://www.comfort-inturkiye.com/dis-hekimligi-2/>. (2020). Comfort-in İğnesiz Enjektor Türkiye Resmi Sayfası. from <http://www.comfort-inturkiye.com/dishekimligi-2/>

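### The trial is split-mouth, but the only test named for comparing the two injection systems is an ANOVA with Tukey that, as written, ignores the pairing within child

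*Protocol*

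**What the plan says.** Section 4 of the protocol (Materials and Methods) states the design: "The groups will be formed according to the split mouth method in the same patient with symmetrical primary molar teeth". Section 4.3 repeats it: "The groups will be formed according to the split mouth method, with symmetrical primary molar teeth in the same patient". The study teeth get Comfort-In and the control teeth the standard injection. Section 2.2.3 confirms that there are two systems: "Complications that may be observed after two different anesthesia systems are applied will be recorded".

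Sections 4 and 4.7 then give the analysis in almost the same words. For the comparison of systems: "Anova test and Post Hoc Tukey test will be used for comparison between groups". For sex, section 4.7 says: "independent two-group t test will be used to evaluate the pain status between male and female patients within the groups". No paired t test, signed-rank test, repeated-measures ANOVA, mixed model or term for child appears anywhere in the protocol.

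On size, section 4.6.1 says: "Considering that 60 people should be included in the study and the possibility of loss, the sample size was determined as 90". It gives alpha 0.05 and power 0.95, but no effect size, SD, within-child correlation or test.

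**The concern.** In this design each child supplies one Wong-Baker and one FLACC score under each system. The relevant variability is that of the within-child difference. An ANOVA between groups uses the spread between children as its error term, which is the variation that a split-mouth design exists to remove. Tukey points to the independent-groups form as well: it is a multiple-comparison procedure and does nothing with two conditions.

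This is the only stated analysis of the trial's main question (section 3.1). If it is carried out literally, the standard error, confidence interval and p value do not match the design. Under positive within-child correlation the interval is too wide and a real difference may be missed. Under negative correlation the type I error exceeds 5%.

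This is more than detail left for an SAP. The protocol names a method twice, and that method does not fit the design it also states twice.

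**Working it through.** **Inputs from the protocol.** Two systems within each child (sections 2.2.3, 4, 4.3); ANOVA with Tukey (sections 4, 4.7); alpha 0.05, power 0.95, 60 required and 90 planned (sections 4, 4.6.1).

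**Assumptions.** Two-sided testing; rho from −0.2 to 0.7; a true difference of 0.3 or 0.5 SD of a single score; equal variances unless stated otherwise. The protocol gives none of these.

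**1. The plan's own figure.** With z(0.975) + z(0.95) = 1.960 + 1.645 = 3.605, the 60 is compatible with several bases:
- 60 pairs: standardised within-child difference 3.605/√60 = 0.47.
- 60 per group: d = 3.605 × √(2/60) = 0.66.
- 30 per group: d = 3.605 × √(2/30) = 0.93 (0.95 with the exact F distribution).

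The basis therefore cannot be identified, and the 60 can be neither reproduced nor refuted. The point does not depend on it.

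**2. What the named test amounts to.** For two groups the ANOVA F test is the independent two-sample t test. Tukey's critical value for two groups at 118 degrees of freedom (2 × 60 − 2), q/√2 = 1.980, equals the t value of 1.980. Tukey therefore adds nothing.

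**3. Standard error.** With n children and common SD σ, the unpaired analysis uses √(2σ²/n). The true value for paired scores is √(2σ²(1 − rho)/n). The ratio is 1/√(1 − rho).

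**4. Type I error.** By normal approximation, the actual size of the unpaired test is 2 × [1 − Φ(1.96/√(1 − rho))]. The simulated column is from 100,000 trials per cell with 60 pairs of bivariate normal scores.

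| rho | SE ratio | Size, formula | Size, simulated |
|---|---|---|---|
| −0.2 | 0.913 | 7.4% | 7.3% |
| 0 | 1.000 | 5.0% | 4.9% |
| 0.3 | 1.195 | 1.9% | 1.9% |
| 0.5 | 1.414 | 0.6% | 0.6% |
| 0.7 | 1.826 | 0.04% | 0.05% |

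The paired test stayed between 4.8% and 5.1%.

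**5. Power, unpaired / paired, same simulation.**

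| Children, true difference | rho 0.3 | rho 0.5 | rho 0.7 |
|---|---|---|---|
| 60, 0.5 SD | 81.7 / 89.6% | 85.6 / 96.8% | 91.1 / 99.9% |
| 90, 0.5 SD | 95.0 / 97.7% | 97.4 / 99.7% | 99.3 / >99.9% |
| 60, 0.3 SD | 34.6 / 48.9% | 31.9 / 62.6% | 28.2 / 84.0% |
| 90, 0.3 SD | 52.3 / 66.4% | 52.5 / 80.5% | 53.2 / 95.2% |

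Another view: choose the true difference so that a paired test has exactly 95% power. The unpaired test then has about 90%, 80% and 51% at rho 0.3, 0.5 and 0.7 (normal approximation).

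**6. Ordinal scores.** Section 2.2.1 says of the Wong-Baker scale: "It consists of 6 face shapes that express the pain condition". A latent normal score was cut into six levels with assumed shares of 30/25/20/13/8/4% (60 pairs, 4,000 trials, latent rho 0.3, 0.5, 0.7). The unpaired test rejected a true null in 1.8%, 0.7% and 0.2% of trials. Power at a latent shift of 0.5 SD, unpaired / paired t / Wilcoxon signed-rank, was 76.1/84.8/84.3%, 79.2/94.0/93.6% and 85.1/99.5/99.3%. The pattern is the same, and the two paired tests are nearly equivalent.

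**7. Unequal variances.** If one arm has twice the SD of the other, the ratio in step 3 becomes √(5/(5 − 4 rho)), which is 1.15, 1.29 and 1.51 at rho 0.3, 0.5 and 0.7. The overstatement shrinks to about 15%, 29% and 51%, in the same direction.

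**The case against.** **The ANOVA may have been meant as repeated-measures.** For two conditions that equals the paired t test, and an SAP could say so. The reading is possible, but the text does not give it, and a comparison between groups with Tukey points the other way. An analyst following the protocol literally would run the independent form, so the sentence needs correcting on either reading.

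**The error runs the safe way, and its size is assumed.** This stands as a limit. Rho, the SD and the effect are not in the protocol. With positive correlation the test is conservative, and with 90 children and a 0.5 SD difference it still has 95% power or more. The large losses need a smaller effect, or fewer children together with high correlation. Nothing in the protocol suggests a negative rho. Even so, the interval and p value are wrong for the design unless rho is zero.

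**Tukey may be wanted for the anxiety aim.** Section 2 also aims to relate anxiety to pain, and anxiety is measured with IDAF-4C. But in sections 4 and 4.3 the groups are the study and control teeth, and no anxiety groups are defined. If such an analysis is intended, it needs its own sentence.

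**Some children may lack a complete pair.** Section 4 removes children from the study for serious pain or insufficient anaesthesia with Comfort-In. That is true, but those children are lost under the current plan too.

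**Conclusion.** The concern holds. The named test does not fit the stated design: it is wrong as written, and should be corrected before analysis. Its size depends on a correlation that the protocol does not give. A positive value is plausible because both scores come from one child; the test is then conservative, and the cost is precision and power. The cost ranges from slight (90 children, 0.5 SD) to severe (at 0.3 SD and rho 0.7, 53% against 95% power with 90 children). At rho zero there is no error. Whether the stated 95% power is missed cannot be determined, because the basis of the 60 is unknown. The independent t test of boys against girls within each system is not affected, since it compares different children.

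**What to change.** In sections 4 and 4.7, replace the ANOVA/Tukey clause with wording such as:

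> Comfort-In and standard injection will be compared within child by a paired t test on the within-child differences, reporting the mean difference with its 95% confidence interval, for Wong-Baker and for FLACC. A Wilcoxon signed-rank test will serve as a sensitivity check because the scores are ordinal. The number of children without both scores will be reported.

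Delete Tukey from the comparison of systems. Keep the independent t test for sex within each system. A repeated-measures ANOVA or a mixed model with child as random effect would also be acceptable, provided it is named as such.

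The cost is one clause changed in two places. Both tests are in SPSS, and the plan already collects a score on each side, so no extra data or visits are needed.

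When the sections are edited, it would help to state which test and which effect the 60 was based on.

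### The boy-girl pain comparison is an unadjusted t test between different children aged 4 to 11; adjusting for the age already recorded could add precision and would guard against confounding by age

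*Protocol*

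**What the plan says.** The Protocol names the test for sex twice. Section 4.7 (Evaluation of Data) says "independent two-group t test will be used to evaluate the pain status between male and female patients within the groups". Section 4 (Materials and Methods) says "an independent two-group t test will be used to evaluate the pain level between male and female patients within groups". Neither sentence names a covariate.

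The inclusion criteria in section 4.3 set the age range: "Between the ages of 4-11". The sociodemographic form described under section 4.6.1 (Components of a Study-Specific Clinical Assessment) "includes information such as age, gender, contact information, and medical condition of the patients", so age is available for every child.

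Section 4.6.1 (General Method) explains why sex is of interest and what is balanced: "Since gender is one of the factors that can affect postoperative pain, female and male patients will be distributed equally". That fixes the numbers of boys and girls. No matching or stratification by age is stated.

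**The concern.** The injection systems are compared by split mouth, so a child's age is the same on both sides and drops out of the mean difference between devices. Sex has no such protection. It is not randomised, and boys and girls are different children, so neither the split-mouth design nor the random allocation of injection balances age between them.

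If pain scores vary with age over this eight-year band, leaving age out has two possible consequences. The age-related spread stays in the error term, so the estimate is less precise than the data allow. And if the boys and girls who enrol, or who remain in the analysis, differ systematically in age, part of an age effect would be reported as a sex effect. What is at stake is the interpretation of one subsidiary comparison.

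**Working it through.** **Inputs from the Protocol.** Ages 4 to 11 (section 4.3); 60 children required and 90 planned, alpha 0.05 (sections 4 and 4.6.1); equal numbers of boys and girls (section 4.6.1). This gives 30 per sex if only the required number remains, or 45 per sex if all 90 do.

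**The plan's own figure.** No power or sample size is stated for the sex comparison. The required 60 is given at power 0.95 without an effect size, SD or test, so it cannot be reproduced. It is used here only to set the number per sex.

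**Assumptions.** Ages spread evenly over the whole years 4 to 11; two-sided 5% tests; a linear relation between age and pain with correlation r. The Protocol gives no value for r, so 0, 0.2, 0.3 and 0.5 are shown.

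**Step 1: age spread and chance gap.** SD of age = sqrt((8² − 1)/12) = 2.29 years. The SD of the boy-girl gap in mean age is 2.29 × sqrt(2/n).
- n = 30 per sex: 0.59 years; 95% range ±1.96 × 0.59 = ±1.16 years.
- n = 45 per sex: 0.48 years; 95% range ±0.95 years.

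**Step 2: does a chance gap break the t test?** In units of the pain-score SD, the variance of the boy-girl difference is 2/n. It splits into r² × 2/n from the chance age gap and (1 − r²) × 2/n from everything else. The t test estimates the whole 2/n, so the chance gap is already in its standard error. In 40,000 simulated trials per setting, the overall type I error of the plain t test was 4.7% to 5.1% for every r and both sample sizes.

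**Step 3: precision.** Adjustment removes a fraction r² of the variance. The simulated power below is for a true sex difference set at (1.96 + 0.84) × sqrt(2/n), that is 0.72 SD at 30 per sex and 0.59 SD at 45 per sex.

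| Assumed r | Variance removed | Power, t test | Power, age-adjusted (30 / 45 per sex) |
|---|---|---|---|
| 0 | 0% | about 79% | about 79% (nothing to remove) |
| 0.2 | 4% | 79% | 80% / 80% |
| 0.3 | 9% | 79% | 82% / 82% |
| 0.5 | 25% | 78-79% | 88% / 89% |

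The row for r = 0 follows from the formula and was not simulated.

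**Step 4: a real age difference between the sexes.** One year of mean age difference shifts the boy-girl difference by r/2.29 = 0.09, 0.13 and 0.22 SD for r = 0.2, 0.3 and 0.5. The standard error is sqrt(2/30) = 0.26 or sqrt(2/45) = 0.21 SD. With a systematic one-year difference and no sex effect, the unadjusted test rejected in 6-7%, 8-9% and 13-18% of simulated trials. The age-adjusted test stayed at about 5%.

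**Step 5: one sample with an unusually large chance gap.** Among simulated trials whose gap fell outside its 95% range (about 1 in 20), the unadjusted test rejected in about 7%, 9-10% and 18-19% for r = 0.2, 0.3 and 0.5, against about 5% adjusted. These rates are conditional on the gap. Samples with smaller gaps offset them, which is why the overall rate in step 2 stays at 5%.

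**The case against.** The strongest objection is that the t test is a valid test of the crude sex difference. A reader might infer that any chance age gap is turned into a false sex effect, so that the plan has an error rate above 5%. Steps 2 and 5 show otherwise: the higher rates hold only given a rare large gap. For the same reason, a chance shift in the difference and a wider standard error are not two separate harms. They are one loss of precision. This part of the objection stands in full.

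A reader might also infer that the sex comparison is confounded by age. The Protocol contains nothing to show that boys and girls differ in age. Enrolment as children present, and the exclusion from the study of children with serious pain or insufficient anaesthesia under the jet injector, are possible routes to a difference, but no more than that.

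The gain is also uncertain. At r = 0.2 it is about one percentage point of power, and at r = 0 there is none. The comparison is subsidiary: the aims and the main purpose concern the injection systems, acceptability, preference and anxiety, not sex.

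Finally, covariates are often left to a statistical analysis plan. Here, however, the Protocol itself fixes the test, twice and without age, so the point concerns a stated method and not an omission. That part of the objection does not stand.

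**Conclusion.** The point holds as a minor improvement. The named test is valid for the crude difference and keeps its overall 5% error rate under chance age gaps. It gives up between none and about a quarter of the variance, for assumed age-pain correlations from 0 to 0.5. It also offers no protection if the sexes differ systematically in age, which the Protocol neither shows nor prevents. The figures rest on evenly spread ages, 30 to 45 children per sex, a linear age effect and an assumed correlation.

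Nothing here touches the conclusion about the injection systems: age is constant within a child and cannot bias that mean difference. This says nothing about the form of the test named for the device comparison, which is a separate matter.

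**What to change.** In section 4.7 and in the matching sentence of section 4, replace the independent t test for sex with a linear model of the pain score on sex and age in years, fitted within each injection group. Report the age-adjusted boy-girl difference with its 95% confidence interval, and tabulate age by sex so that the reader can see whether the sexes differ.

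The cost is one degree of freedom per model and the assumption that age acts linearly, with the same slope in both sexes, on scores such as the six-face Wong-Baker scale. No extra data, children or software are needed: age is already on the form, and the model runs in the SPSS package named in the Protocol.
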